### **8.2 Populations for Analyses**

The study analyses will be performed at the termination of the study; once the last visit of the last patients has been recorded. The analyses will be performed on the 64 SLE patients enrolled in the study based on the inclusion and exclusion criteria as stated above.

### **8.3 Endpoint Definitions**

Starting at baseline and at each visit, the SLEDAI 2K, BILAG, and joint count will be recorded. In addition the patient and physician Global Assessment will be recorded. These are all validated measures to evaluate SLE disease activity and response to therapy. In addition, the US 28-joint synovitis and power Doppler scores will be compared to baseline.

### ***8.3.1 Demographics and Baseline Characteristics***

All subjects who receive a dose of study drug will be evaluated for safety. Safety outcomes include adverse events, clinically significant changes in vital signs, laboratory test abnormalities, and clinical tolerability of the drug. The investigator will determine the severity of each adverse event as mild, moderate, severe, or very severe. Descriptive statistics (mean, standard deviation, median, inter-quartile range, and frequency distribution) of safety data will be generated to characterize the study participants by treatment arm. The Chi-square test or Fisher's exact test will be used to compare the percent of subjects presenting with AEs (analyzed separately as SAE, any AE) between the two groups.

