### **STUDY IN SYSTEMIC LUPUS ERYTHEMATOSUS**

In NCT 001 10678, A phase IIb study in SLE was conducted and published. 118 patients were treated with 10mg/kg abatacept i.v. in the standard RA dose, and 57 with placebo. 65% completed 12 months of study. The primary outcome, rate of flare beginning after prednisone taper, over a total of 12 months, measured by adjudicated BILAG A and B, did not show significant differences between the groups. However, patients with lupus polyarthritis at entry had significantly fewer flares compared to placebo in both BILAG A flare (36.5% in placebo vs 12.5% in abatacept) and physician-identified flares. The incidence of serious adverse events was higher in abatacept (19.8%) vs placebo (6.8%) without any particular type of SAE identified.

In a recent study in patients with lupus nephritis, 198 individuals were treated with abatacept i.v.. for 12 months (one group with a loading dose of 30 mg/kg once a month x3 followed by 10 mg/kg monthly; a second with 10 mg/kg monthly i.v. for the entire 12 month period). At 12 months, there were no statistically significant differences in response rates (defined as complete renal response or partial- plus- complete renal responses) between the group that received placebo infusions plus standard care compared to either of the groups that received abatacept plus standard care. The occurrence of severe adverse events did not differ significantly between the groups: SAEs occurred in 28-33.3% of the abatacept groups and 31% of the placebo group. There were 7 deaths in the abatacept groups (one of which was a gunshot wound) for a rate of 2.5%, with 7 deaths in the placebo group for a rate of 7%. Treatment related SAEs occurred in 19-20% of the abatacept groups and 15% of the placebo groups.

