Abatacept, a selective costimulation modulator, is a soluble fusion protein that consists of the extracellular domain of human cytotoxic T-lymphocyte (T-cell)-associated antigen 4 (CTLA-4) linked to the modified Fc (hinge, CH2, and CH3 domains) portion of human immunoglobulin G1 (IgG1). An intravenous (IV) formulation of abatacept is approved in several countries including the United States and in the European Union (EU) for the treatment of moderate to severe rheumatoid arthritis (RA) in adults. The subcutaneous preparation is currently approved in the United States for rheumatoid arthritis in adults. Based on the clinical trial experience in adults, the risks that may be associated with the use of abatacept include infections, some of which may be serious or fatal, infusion related reactions, and an increase in respiratory adverse events and infections in patients with chronic pulmonary obstructive disease (COPD). Other potential risks may include the development of malignancies or autoimmune disorders, but an increased risk of these types of events has not been observed. As with the use of any protein therapeutic, antibodies against abatacept (immunogenicity) may develop. The rate of immunogenicity has generally been low and there has not been an apparent effect on safety, efficacy, or pharmacokinetics (PK). Abatacept intravenous is also currently approved for the treatment of moderately to severely active polyarticular juvenile idiopathic arthritis (JIA) in pediatric patients 6 years of age or older in several countries including the USA for patients aged 6 - 17 years old. Abatacept was generally safe and well tolerated in subjects with JIA.

For the period from the fourth quarter of 2005 to the third quarter of 2009 inclusive, the total number of patients exposed to abatacept is estimated to be equivalent to 60,225 patient-years of exposure. The overall pattern of safety reporting raises no new safety concerns. A subcutaneous (SC) formulation of abatacept is being studied for the treatment of a number of immune mediated disorders; results from 3 completed clinical studies in RA are included in this document.

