### **5.6 Management of Possible Acute Hypersensitivity Reactions to Abatacept**

Hypersensitivity or acute allergic reactions may occur as a result of the protein nature of abatacept. The following information is provided to assist in the recognition of hypersensitivity reactions and in the management of those reactions should they occur during or after the administration of study drug. Care should be taken to treat any acute toxicities expeditiously, should they occur.

Signs and management of potential acute hypersensitivity reactions:

Sign	Management
Symptomatic Hypotension	Discontinue the abatacept injection if it has not been completed. Place the subject in the Trendelenburg position and administer IV fluid. Administer epinephrine, glucocorticoids, antihistamines, and pressor agents as indicated. Since injections will be self-administered after the initial dose, the subject will have emergency contact information for all the physician investigators participating in this trial. We will also ensure that patients have immediate emergency access to a local physician (if they live more than 20 miles away from the UCLA Medical Center) and Emergency Room.
Dyspnea	Discontinue the abatacept injection. Observe the subject for worsening of the event and for the appearance of additional signs and symptoms of anaphylaxis. Administer antihistamines, epinephrine, and glucocorticoids as indicated. Since injections will be self-administered after the initial dose, the subject will have emergency contact information for all physicians participating in this trial. We will also ensure that patients have immediate emergency access to a local physician (if they live more than 20 miles away from the UCLA Medical Center) and Emergency Room
Acute Pain in Chest, Back or Extremities	These are potential signs of anaphylaxis. Follow the same treatment regimen as is used to treat dyspnea.
Chills, Fever, Urticaria, or Generalized Erythema	These may be signs of an allergic reaction to protein products. Treat by administration of acetaminophen and antihistamines.

Because abatacept has immunomodulatory activity, subjects may be at increased risk of infectious complications. Significant infectious complications should be treated appropriately. Study medication should be withheld, and restarted only when the infection is clinically resolved.

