## 7 ADVERSE EVENT REPORTING

### 7.1 Adverse Events

An **Adverse Event (AE)** is defined as any new untoward medical occurrence or worsening of a pre-existing medical condition in a patient or clinical investigation subject administered an investigational (medicinal) product and that does not necessarily have a causal relationship with this treatment. An AE can therefore be any unfavorable and unintended sign (including an abnormal laboratory finding, for example), symptom, or disease temporally associated with the use of investigational product, whether or not considered related to the investigational product.

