#### 7.1.1 Serious Adverse Events

A **Serious Adverse Event (SAE)** is any untoward medical occurrence that at any dose:

- results in death
- is life-threatening (defined as an event in which the subject was at risk of death at the time of the event; it does not refer to an event which hypothetically might have caused death if it were more severe)
- requires inpatient hospitalization or causes prolongation of existing hospitalization (see note below for exceptions)
- results in persistent or significant disability/incapacity
  - is a congenital anomaly/birth defect
  - is an important medical event (defined as a medical event(s) that may not be immediately life-threatening or result in death or hospitalization but, based upon appropriate medical and scientific judgment, may jeopardize the subject or may require intervention [eg, medical, surgical] to prevent one of the other serious outcomes listed in the definition above.) Examples of such events include, but are not limited to, intensive treatment in an emergency room or at home for allergic bronchospasm; blood dyscrasias or convulsions that do not result in hospitalization.) Potential drug induced liver injury (DILI) is also considered an important medical event. (See Section 6.6 for the definition of potential DILI.)

Suspected transmission of an infectious agent (eg, pathogenic or nonpathogenic) via the study drug is an SAE.

All pregnancies, regardless of outcome, must be reported to BMS, **including pregnancies that occur in the female partner of a male study subject. All pregnancies must be followed to outcome.** See Section 7.6 for instructions on reporting pregnancies.

Although pregnancy, overdose, cancer, and potential drug induced liver injury (DILI) are not always serious by regulatory definition, these events must be handled as SAEs and should also be reported to BMS in an expedited manner, as described in Section 7.2.

**NOTE:** The following hospitalizations are not considered SAEs in BMS clinical studies:

- a visit to the emergency room or other hospital department lasting less than 24 hours that does not result in admission (unless considered an “important medical event” or a life-threatening event) or administration of intravenous antibiotics
- elective surgery planned before signing consent
- admissions as per protocol for a planned medical/surgical procedure

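### The any-AE comparison in section 8.3.1 can hide a possible infection excess on abatacept, because lupus worsening counts as an AE and infections have no comparison of their own

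*Combined protocol and SAP*

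**What the plan says.** The safety analysis text stands in section 8.3.1, under the demographics heading. It names a chi-square or Fisher's exact method, whose purpose is to "compare the percent of subjects presenting with AEs (analyzed separately as SAE, any AE) between the two groups". The same paragraph adds that "Descriptive statistics (mean, standard deviation, median, inter-quartile range, and frequency distribution) of safety data will be generated" by treatment arm, without naming any event category. Section 8.4.4 (Other Analyses) plans nothing further.

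Section 7.1 defines an AE as "any new untoward medical occurrence or worsening of a pre-existing medical condition". Section 7.1.1 makes an event serious if it leads to admission, and its list of exempt hospitalizations does not include lupus flares. Every patient enters with active lupus arthritis (section 4.2.1), so a worsening during the study meets the AE definition.

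On infection, section 1.4 says that "the risks that may be associated with the use of abatacept include infections, some of which may be serious or fatal", and section 5.6 says that "subjects may be at increased risk of infectious complications". Neither gives a rate by arm.

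**The concern.** The any-AE percentage adds together components that need not move in the same direction. Flares should be fewer on abatacept if the drug works: section 8.1 assumes 67% vs 30% response. The account of the phase IIb SLE trial reports BILAG A flares in 12.5% of abatacept and 36.5% of placebo patients in the polyarthritis subset. Infections may be more frequent on abatacept. Background events unrelated to either push both arms towards a high common percentage.

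A small any-AE difference could therefore come from no added toxicity, or from added infections offset by prevented flares and diluted by everything else. The tested result cannot separate the two, and the offset grows with the drug's efficacy. Infection, the first risk listed in section 1.4, has no named comparison that would settle the question.

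**Working it through.** **The plan's own figure.** Section 8.1 gives n = 28 per group for 67% vs 30%, p = 0.05, power 0.8. With the two-sided pooled normal formula, n = [1.96·√(2·0.485·0.515) + 0.842·√(0.67·0.33 + 0.30·0.70)]² / 0.37² = 27.4, so 28. The figure reproduces. It concerns the primary endpoint only; no power or precision is stated for safety.

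**Inputs from the documents.** 32 patients per arm (section 8.1); 12-month flare rates of 36.5% placebo and 12.5% abatacept (account of the phase IIb SLE trial).

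**Assumptions.** Constant flare hazard; flares, infections and background AEs independent; every flare recorded as an AE; infection and background AE rates chosen for illustration.

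**Step 1: flare rates at 16 weeks.** f = 1 − (1 − f₁₂)^(16/52).
- Placebo: 1 − 0.635^(16/52) = 13.0%.
- Abatacept: 1 − 0.875^(16/52) = 4.0%.

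**Step 2: infection excess that is fully cancelled.** With background rate b and infection rate i, P(any AE) = 1 − (1 − b)(1 − i)(1 − f). Setting the arms equal, b drops out and the break-even excess is (1 − i_P)(f_P − f_A)/(1 − f_A) = (1 − i_P) × 0.0902/0.9597.

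| Placebo infection rate | Excess fully cancelled |
|---|---|
| 5% | 8.9 points |
| 10% | 8.5 points |
| 15% | 8.0 points |
| 20% | 7.5 points |
| 30% | 6.6 points |

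That is 2 to 3 patients of 32.

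**Step 3: a larger excess.** Assume infections of 30% vs 45% (+15 points) and 50% background AEs.
- Without flares: placebo 1 − 0.5·0.70 = 65.0%; abatacept 1 − 0.5·0.55 = 72.5%; difference +7.5.
- With flares: placebo 1 − 0.5·0.70·0.870 = 69.6%; abatacept 1 − 0.5·0.55·0.960 = 73.6%; difference +4.0.

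For background rates from 0% to 70%, the difference with flares runs from +8.1 to +2.4 points.

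**Step 4: what each component costs.** Exact two-sided Fisher power at 32 vs 32, counting only rejections with more events on abatacept, with 50% background AEs:

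| Assumed infections | Infections alone | Any AE, no flares | Any AE, with flares |
|---|---|---|---|
| 15% vs 45% | 69% | 17.5% | 9.8% |
| 30% vs 45% | 17% | 6% | 3% |

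At this background rate dilution does more damage than flares: in Step 3 it removes 7.5 of the 15 points, and flares remove a further 3.5.

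**Step 5: precision of a separate infection row.** At 30% vs 45% the approximate 95% half-width is 1.96·√[(0.45·0.55 + 0.30·0.70)/32] = 23 points.

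**The case against.** The strongest case against is that infections would not be hidden. Section 8.3.1 plans frequency distributions by arm, section 7.3 records diagnosis, seriousness and relationship for every AE, and the monitoring board reviews AEs and SAEs by coded group each quarter (sections 3.4, 6.3 and 7.3). No section says that a non-significant any-AE test will be taken as evidence of no added harm. All of this is correct, and it limits the point to one about specification. It does not remove it: no event category is named, so an infection row is not assured and could be chosen after unblinding.

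Four stronger readings are tempting but not supported.

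- **That an infection excess is established.** Sections 1.4 and 5.6 speak only of possible risk. Section 1.3.4 reports that infections were not more common on abatacept after single subcutaneous doses in healthy subjects (40 abatacept, 8 placebo).
- **That any AE would favour abatacept despite a 15-point infection excess.** With 12-month flare rates, 30% vs 45% infections and no background AEs, any AE is 55.6% placebo vs 51.9% abatacept. Those flare rates belong to a trial three times as long. At 16-week rates the difference stays positive.
- **That SAEs cancel in the same way.** Section 7.1.1 makes this possible, but the phase IIb SLE trial had more SAEs on abatacept (19.8% vs 6.8%). Those rates are for the whole trial and the flare rates for a subset, so this is not a direct test; still, nothing in the documents shows cancellation.
- **That removing lupus events would repair the comparison.** Step 4 shows otherwise. Section 1.4 also lists autoimmune disorders as a potential risk, so lupus worsening could itself be harm and the all-event comparison should stay.

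**Conclusion.** The point holds as a gap in the pre-specified safety analysis. The only tested measures are any AE and SAE. The first mixes events expected to fall on abatacept with events that may rise, and background AEs dilute both. At flare rates scaled to 16 weeks, an infection excess of about 7 to 9 points disappears entirely from the any-AE difference, and an assumed 15-point excess is reduced to about 4 points. These sizes depend on assumed infection and background rates, constant hazard, independence and full recording of flares as AEs. They show what the comparison could miss, not what will occur. The main gain comes from looking at infections separately; excluding lupus events is a useful second view.

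**What to change.** In section 8.3.1, keep any AE and SAE and add, by arm:

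- (a) any infection and any serious infection;
- (b) any AE and any SAE, excluding events recorded as SLE activity or arthritis worsening.

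Report each with a risk difference and exact 95% confidence interval. Classify events from the diagnoses already recorded under section 7.3, before the code is broken, by a rule written in advance.

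State the counting window and make it match the collection rules. Section 7.3.1 ends routine SAE collection 30 days after the last dose, while section 6.1 places the AE call at week 24, and section 6.3 has SAEs reported up to and including follow-up visits. A single window needs these passages reconciled.

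The cost is analysis-plan wording, a few table rows and a short blinded classification, with no new visits or data items. A few events will need judgement. The estimates will be imprecise at 32 per arm (about ±23 points in the example), so the intervals should carry the interpretation rather than a test.

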### ***8.4.3 Efficacy Analyses***

The Fisher's exact test will be used to compare the percent of subjects achieving primary and secondary outcomes between two groups. Wilcoxon rank sum tests will be used to compare ordinal and quantitative outcomes between groups. Logistic regression will also be used to adjust for baseline clinical presentation and demographic factors. A site by treatment interaction effects will be included in the model to account for possible differences in treatment efficacy between our two sites. Bivariate analysis and nonparametric analysis (for example local polynomial regression or generalized additive model analysis) will be carried out to inspect the relationship between outcome and covariates. The goodness-of-fit of logistic models will be evaluated using the Hosmer-Lemeshow test. With the quantitative outcomes such as joint counts, ultrasound measurements, etc we will use Poisson regression to assess the treatment effect or linear regression for continuous outcomes. Poisson regression is a special case of generalized linear model and robust pseudo likelihood inference will be used in the analysis. We also will use multiple imputation technique to accommodate possible missing data at 12 and 24 weeks due to patients lost to follow up. The imputation model will include all baseline 12 week and 24 week outcomes and covariates to impute the missing outcomes . Analyses will be done with and without imputation.

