Study Design:	Randomized trial of 32 SLE patients treated with subcutaneous abatacept 125mg sq once a week vs. 32 placebo treated subjects over a 16 week period. Patients will be seen every 4 weeks from baseline. One half of patients will be recruited at UCLA and one-half at UCSD. We expect 30 patients in each group to complete the 16 week study.
Study Schema Drugs / Doses / Length of Treatment)	Abatacept 125 mg or placebo will be administered subcutaneously once a week for 16 weeks. There will be a telephone follow up 2 months after the last injection to capture post-treatment adverse events.
Accrual Goal: (Total number of subjects)	64 (32 at UCLA and 32 at UCSD)
Accrual Rate: (Number of subjects expected per month)	2-3 subjects per month at each site
FPFV: April 1, 2015 LPFV: March 31, 2018  Follow Up: 16 weeks per patient plus 8 weeks of observation for adverse events	
Correlative Studies: These will be performed at the UCLA site only	
1) Biomarkers: a) T cell numbers and phenotypic and functional characteristic in PBMC measured at week 0 and 16. These will include for T cells CD4+, CD3+, CD25+, CD8+, Foxp3+ and cytoplasmic stains for IFNgamma, IL2, IL-17, IL21 and IL-10.
 
b) B cell numbers and subsets, including naïve, activated and plasmablasts.
 
c) Ability of autologous CD4+CD25hi T cells to suppress proliferation of CD4+CD25- T cells.
 
d) Cytokines in serum: IFNgamma, IL-6, IL-10, IL-17, IL23 and BLyS
 
2) Ultrasound with power Doppler of joints assessing synovitis, tenosynovitis (18 joints) and erosions at week 0 and 16.

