Inclusion Criteria	
 
1. Meet at least 4 of the 11 American College of Rheumatology (ACR) 1997 criteria for classification of SLE (see Appendix 1). OR meet the recent classification recommended by SLICC (Appendix 2)
 
2. <math>\geq 3</math> swollen and tender joints on 2 examinations at least 2 weeks apart and no more than 8 weeks apart.
 
3. SLEDAI2K score <math>\geq 4</math> indicating active disease.
 
4. Documented positive ANA (<math>\geq 1:80</math>) and/or anti-dsDNA during course of SLE.
 
5. Men and women, at least 18 years of age. Women of childbearing potential must use adequate method(s) of contraception to avoid pregnancy throughout the study and for up to 2 months after last study drug dose. They must have a negative serum or urine pregnancy test prior to the start of study medication.
 
6. Background therapies allowed: antimalarials (dose constant for <math>\geq</math> one month before study entry and during 16 weeks of trial), methotrexate (same criteria as for antimalarials), azathioprine (same criteria), mycophenolate (same criteria), leflunomide (same criteria). During the screening period and for up to 6 weeks after randomization, a daily prednisone (or equivalent) regimen of up to 20 mg daily may be initiated to treat the moderate to severe disease activity present at screening. The initial steroid regimen is not required if investigators or patients believe that the risks would outweigh the potential benefits. Patients who do not take any glucocorticoids during the study will be included in the treatment groups and analysis.
 
 
*Steroids should be tapered to a target dose of no more than 10 mg/day of prednisone (or equivalent) by the end of Week 8 (Day 56). The steroid regimen should be tapered as quickly as safely possible. Prednisone dose requirements higher than 10 mg daily at the 8 week visit will cause the patient to be ruled a non-responder for the abatacept treatment arm.

---------------------------	--

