#### **Baseline Visit (Visit 1)**

The following procedures/assessments will be performed at Baseline Visit (Visit 1)

- Patient Global Assessment
- SF 36 and fatigue scale questionnaire

- Concomitant medications
- Adverse events
- Physical Examination
- Vital signs (temperature, pulse, systolic, and diastolic blood pressure) and weight
- 28 Tender and Swollen Joint Count
- Urine pregnancy test (beta-hCG) for all women of child-bearing potential. In case of positive result, the subject will not be eligible to participate in the study and will be considered as a Screening failure.
- Review all laboratory assessments for subject safety/clinical significance
- Review all inclusion exclusion criteria including compliance with allowed concomitant medications prior to Baseline and assess subject's final eligibility.
- Bilateral Posterior-Anterior (PA) hand x-rays (including wrists) should be performed for eligible subjects (unless already performed within 4 weeks prior to Baseline)
- Joint Ultrasound (18 joints: 2-5PIPs, 2-5 MCPs and wrists, bilaterally)
- SLEDAI 2K
- BILAG 2004
- Physician Global Assessment
- Safety Laboratory Testing (hematology and biochemistry)
- Urinalysis
- Immunology assessments (C3, C4, IgG)
- Lupus Biomarkers; IFN gamma, IL10, TGFbeta, IL17, IL23 and BLyS levels.
- T and B cell studies
- First dose administration of Study drug. The subject should stay at the study site for 1 hour following the administration of the first dose.
- Subjects will be given all the necessary supplies and detailed instructions for administration of study drug. In addition, subjects will be instructed to contact the study center if any questions or problem arise.
- Instruct subjects to complete study drug dosing diary for accountability and compliance.

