## **8 STATISTICAL CONSIDERATIONS**

### **8.1 Sample Size Determination**

We based our sample sizes on the preliminary data (unpublished): SLE patients with arthritis at the start of a treatment had a mean score on 66-joint count of  $21 \pm 8.2$ . There was a decrease to a mean of  $2.0 \pm 1.5$  after 12 weeks of various interventions in patients who reported they improved. For the study proposed here, if 67% of abatacept pts will achieve 20% improvement in swollen and tender joints vs. 30% of controls by week 16, n=28 per group (with p=0.05, power=0.8). Thus we plan 32 patients for abatacept over 16 weeks and 32 patients for placebo over 16 weeks, a total of 64. The dropout rate in the abatacept non-nephritis lupus trial was 35% (over 12 months). We anticipate one-third that in a 4 month trial, proposed, here – i.e. 12%. If we begin with 64 patients we should have 56 completers, thus approximately 28 in each group.

Thus, we will plan to recruit 32 SLE patients at UCLA and an additional 32 at UCSD (separate contract).

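### The primary responder comparison is an unadjusted Fisher's exact test with about 71% power at 28 completers per group, not the stated 80%, and no pre-specified adjusted analysis is made primary

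*Combined protocol and SAP*

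**What the plan says.** The primary outcome (Sections 2.1 and 6.4.1) is the proportion of patients with at least 20% improvement in the 28-joint tender and swollen count at week 16. Section 8.4.3 gives the test: "The Fisher's exact test will be used to compare the percent of subjects achieving primary and secondary outcomes between two groups". It then adds: "Logistic regression will also be used to adjust for baseline clinical presentation and demographic factors". That model also carries a site-by-treatment interaction. Its covariates are not listed, and the section does not say which of the two analyses decides the trial.

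Section 8.1 gives the sizing assumption, "if 67% of abatacept pts will achieve 20% improvement in swollen and tender joints vs. 30% of controls by week 16", and the result, "n=28 per group (with p=0.05, power=0.8". The enrolment follows: "Thus we plan 32 patients for abatacept over 16 weeks and 32 patients for placebo over 16 weeks, a total of 64". Section 8.1 expects about 28 completers per group, the synopsis expects 30, and Section 8.2 says all 64 enrolled patients will be analysed.

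The data for an adjusted comparison are already in the schedule. The baseline visit in Section 6.1 includes "28 Tender and Swollen Joint Count" and a record of concomitant medication. Site is known: "One half of patients will be recruited at UCLA and one-half at UCSD". On prednisone, the synopsis says that during screening and for a limited time after randomisation "a daily prednisone (or equivalent) regimen of up to 20 mg daily may be initiated".

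**The concern.** Two things are at stake. First, the test that was named is not the test that the sample size fits. Fisher's exact test is conservative in small samples, so the stated 80% may not be what the trial has.

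Second, the primary comparison uses nothing but the 2x2 table, although there is reason to expect some baseline data to predict response. Entry requires only 3 swollen and tender joints. On a count of 3, losing one joint is a 33% improvement, while a patient with many joints must clear several to pass 20%. Entry prednisone may matter too: it can lower the count, and the synopsis and Section 4.1 treat a requirement above 10 mg daily at week 8 as failure. With about 30 patients per arm, using such information could sharpen the comparison at no cost in patients.

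The adjusted model does not fill this role as written. It is an addition, its covariates are open, and its interaction term makes the meaning of the treatment coefficient depend on how site is coded.

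**Working it through.** **Inputs.** From Section 8.1: 67% versus 30%, 5% level, 80% power, 28 per group, 32 per group enrolled, 12% dropout. Sidedness is not stated. Two-sided is assumed because it reproduces 28, whereas one-sided gives 22 (27 with continuity correction).

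**1. Reproduce the plan's figure.** For the uncorrected z-test with pooled variance, the mean rate is (0.67 + 0.30)/2 = 0.485, and

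n = [1.960·√(2·0.485·0.515) + 0.842·√(0.67·0.33 + 0.30·0.70)]² / 0.37² = (1.385 + 0.553)² / 0.1369 = 27.4, so 28.

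The formula gives 80.8% power at 28. Dropout: 28/0.88 = 31.8, so 32. The plan's figures reproduce. With continuity correction, which approximates Fisher's test more closely, the same inputs give 33.

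**2. Exact power of the named test.** Sum the product of the two binomial probabilities over all tables with a two-sided p-value of at most 0.05.

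| Evaluable per group | z formula | Pearson, exact | Fisher, exact |
|---|---|---|---|
| 28 (Section 8.1) | 80.8% | 79.9% | 71.3% |
| 30 (synopsis) | 83.6% | 84.2% | 76.8% |
| 32 (all enrolled) | 85.9% | 87.8% | 81.7% |

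Fisher's power is still just under 80% at 31 per group (79.35%) and first passes it at 32, which leaves nothing for dropout.

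**3. How much is conservatism.** At 28 per group Fisher's actual size is 2.7% at a common rate of 30% and 2.3% at 48.5%. Pearson's is 5.2% and 4.5%. The power difference, 79.85 − 71.30 = 8.55 points, involves no covariate at all.

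**4. How much covariates could add.** Let ρ be the within-arm correlation between the covariates and response (assumed). Adjustment cuts the variance by the factor 1 − ρ², so replace n by 28/(1 − ρ²) in the z formula.

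| ρ | 28/(1 − ρ²) | Power | Gain over 80.8% |
|---|---|---|---|
| 0.2 | 29.2 | 82.5% | 1.7 |
| 0.3 | 30.8 | 84.5% | 3.7 |
| 0.4 | 33.3 | 87.4% | 6.6 |
| 0.5 | 37.3 | 90.9% | 10.1 |

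A separate simulation of adjusted logistic regression put the covariate part at 1 to 3 points for a weakly prognostic score (SD 0.5 on the logit scale) and 6 to 8 for a moderate one (SD 1.0). About 1 to 10 points is a fair summary for ρ of 0.2 to 0.5. The gain reaches 5 points only at ρ of about 0.35.

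**5. The proposed test.** A re-randomisation test of the covariate-adjusted difference was simulated with one covariate (2,000 trials per setting). For ρ of 0, 0.2, 0.3, 0.4 and 0.5:

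- 28 per group: 79.0%, 81.7%, 84.9%, 85.9%, 90.7%
- 32 per group: 84.6%, 86.7%, 87.4%, 90.8%, 93.8%

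A version with three covariates, re-randomised within site, gave about 79 to 91% at 28 per group and 83 to 94% at 32, with size 4 to 5%. None of these runs included missing data.

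**6. The interaction term.** In simulation at 28 per group, with site dummy-coded and its interaction in the model, the treatment coefficient is the effect at one site and its power is only 48 to 66%. With effect coding, the Wald test of the overall effect has 79 to 91%. Likelihood-ratio tests with three covariates had size of about 6 to 8%, which is a reason to take the p-value from re-randomisation.

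**The case against.** Fisher's exact test is valid and holds the type I error. Chance imbalance after randomisation is already allowed for in its error rate and is not bias. A supporting adjusted model is planned. If all 64 patients are analysed, as Section 8.2 says, Fisher's power is above 80%. All of this stands. It makes the point one of efficiency and specification, not of validity. The 32-per-group figure does require that imputed or otherwise handled dropouts leave the 67% and 30% undiluted, and Section 8.1 itself counts on 28 completers per group.

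A reader might infer that ignoring joint count, prednisone and site costs the whole gap between Fisher's test and an adjusted test at 28 per group, about 8 to 19 points (79.0 − 71.3 = 7.7; 90.7 − 71.3 = 19.4). The documents do not support that. The lower end appears when the covariates predict nothing, so it is Fisher's conservatism. The upper end needs ρ = 0.5, which corresponds to covariates explaining about 42 to 43% of the variation in an underlying continuous response, and nothing in the documents indicates such strength. Percentage change already scales by the baseline count, and a baseline prednisone value misses steroid use started later. At 32 per group the whole gap is about 2 to 12 points.

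A reader might also infer that the plan ignores baseline factors and site altogether. It does not: Section 8.4.3 adjusts for them in the additional logistic model. The gap is that this model is not fully specified and is not named as decisive.

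**Conclusion.** The point holds in this form. At the plan's own rates and 28 completers per group, the test named for the primary outcome has 71.3% power, 8.7 points below the stated 80%. Nearly all of that shortfall is Fisher's conservatism. A pre-specified adjusted test would recover it and could add about 1 to 10 points.

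The Fisher figures rest only on the plan's inputs and a two-sided 5% level. The covariate gain rests on an assumed correlation of 0.2 to 0.5 and should always be quoted with that range. If all 64 are analysed without dilution, there is no shortfall against 80%, and only the smaller efficiency gain remains. The change is worth making because it is cheap and because it settles in advance which analysis decides the trial.

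**What to change.** In Section 8.4.3:

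- Name one covariate-adjusted comparison of week-16 response as primary, with baseline tender plus swollen 28-joint count, pre-dose baseline prednisone and site as main effects, and no site-by-treatment interaction.
- Report the standardised difference in response proportions with its confidence interval. Take the p-value from a re-randomisation test that follows the actual allocation scheme, within site if assignment was made within site. The copy reviewed shows no text under Section 5.2, so the scheme must be confirmed first.
- Apply the same model with and without imputation. The imputation sentence refers to weeks 12 and 24 and should cover week 16.
- Move the site-by-treatment interaction to a secondary analysis.
- Keep Fisher's exact test as a sensitivity analysis, and restate its power in Section 8.1 as about 71% at 28 per group.

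Cost: SAP wording and a little more programming, before unblinding. No new data or patients are needed. The headline analysis becomes slightly less simple than a 2x2 table.
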